6.4 SUBJECT REMOVAL FROM CLINICAL TRIAL

Although all subjects are informed of their right to withdraw from the clinical trial at any time, it is anticipated that such withdrawals will be infrequent. All measures should be taken by the Investigator and his/her staff to encourage subjects to return for required follow-up visits. The clinical trial objectives may be jeopardized if large numbers of subjects are lost to follow-up.

All subjects are expected to continue in the trial until the Sponsor notifies the Investigator in writing that further follow-up is no longer required, except in the event of death or upon the subject's written request for early withdrawal from the clinical trial. A copy of such requests will be kept with the source documentation.

A subject will be considered "*lost to follow-up*" and terminated from the trial when all of the following criteria are met:

- Failure to complete two consecutive visits without due cause
- Documentation of three unsuccessful attempts on three different dates over a period of at least 1 month by the Investigator or designee to contact the subject or next of kin.

All subjects who receive a commercial (a non-trial) heart valve and any subjects who have the EDWARDS INTUITY heart valve explanted will be followed through the end of the trial. Subjects previously exited from the trial due to receiving a commercial valve (at any time point) will be contacted and a request will be made to have them re-consented and reenrolled in the trial and followed through the end of the trial.

6.5 TRIAL TERMINATION

If the Sponsor and/or the Principal Investigator should discover conditions arising during the trial that indicate that the trial should be terminated prematurely, an appropriate schedule for termination will be instituted. All trial subjects enrolled at the time the trial is terminated, will be followed by the Clinical Investigator for a period of five (5) years from the date of enrollment.

The trial plan includes continued annual follow-up until 5 years of follow up are completed on all subjects enrolled in the clinical trial.

6.6 INVESTIGATIONAL DEVICE MANAGEMENT

At the time of this protocol revision, all subjects were enrolled in the trial. Unused devices were returned to the Sponsor and investigational device reconciliation was complete. For a description of investigational device management, please refer to a previous version (Revision N) of the TRANSFORM™ Protocol

7.0 SAFETY ASSESSMENTS

Safety assessments will include examination and reporting of adverse events, ECGs, laboratory parameters, vital signs and any changes from baseline.

Adverse events, whether observed by the Investigator or reported by the subject, will be recorded on the Adverse Event CRF. At each visit, the Investigator or designee will determine whether any adverse events occurred by evaluating the subject. Adverse events may be observed directly, reported spontaneously, or identified by questioning the subject at each trial visit. Questioning subjects should be in a general way, without asking about the occurrence of any specific symptoms. The Investigator must appraise all trial related laboratory values. The Investigator should follow subjects with adverse events until the event has resolved or the condition has stabilized.

CONFIDENTIAL AND PROPRIETARY DATA: This document and the information contained herein may not be reproduced, used, or disclosed without written permission from Edwards Lifesciences LLC

Pre-existing medical conditions or symptoms reported prior to device implant will not be recorded as an AE. In the event there is worsening of a pre-existing medical condition or symptoms following the index procedure, then an AE must be recorded. The adverse event report should note the existence of pre-index procedure history when appropriate.

7.1 SAFETY PROCESS

The Safety Process in the TRANSFORM™ Trial has been established with three (3) levels of independent review of reported clinical outcomes (Adverse Events; AE) conducted by Data Monitoring Committee (DMC), Sponsor's Safety Department (HVT Safety), and an independent Clinical Endpoints Committee (CEC).

Data Monitoring Committee (DMC): The DMC provided a consistent, independent review of clinical outcomes reported in TRANSFORM™ trial during the enrollment period. The Committee will also review the data at the end of the study follow-up. The DMC reviews data reported from the sites, along with CEC-adjudicated data and Echo Core Lab data, and identifies any potential safety issues such as higher than expected SAE and/or death rates, Unanticipated Adverse Device Effects (UADE), or hemodynamic performance that is substantially worse than expected, to determine if the trial should be stopped, suspended, or modified at any time, as specified in the DMC Charter.

Sponsor's Safety Department (HVT Safety): HVT Safety provides an initial review of new adverse events directly following notification that an event has occurred. The review includes a Serious Adverse Event (SAE) and UADE assessment and reporting to the relevant regulatory or trial groups, within the appropriate time frame, in accordance with the applicable regulatory requirements which include, 21 CFR Part 812 (Investigational Device Exemptions), 21 CFR Part 814 (Premarket Approval of Medical Devices), MEDDEV 2.7/3 (Clinical Investigations: Serious Adverse Event Reporting, 2010), and ISO 14155:2011 (Clinical Investigation of Medical Devices for Human Subjects), as well as with the Sponsor's internal standard operating procedures.

Clinical Endpoints Committee (CEC): The primary role of the CEC is to review (adjudicate) and decide on safety endpoints which will be included in the final analysis. The adjudication process and the events selection is based on the approved study endpoints definitions and the CEC Charter. HVT Safety may also include events determined to be possibly related to a safety endpoint during their initial review of the event. Events designated as requiring CEC review are forwarded with relevant source documentation to the CEC by HVT Safety. The CEC can also identify additional events, not previously reported, during their review. These events will also be adjudicated.

7.2 ADVERSE EVENTS

An adverse event (AE) is defined as any untoward medical occurrence, unintended disease or injury, or untoward clinical event in a subject, whether or not related to the investigational medical device. Note: A procedure is not an AE, but the reason for the procedure may be an AE.

7.3 SERIOUS ADVERSE EVENTS

A serious adverse event (SAE), defined as an event that leads to one of the following:

- death;
- a serious deterioration in the health of the trial subject that:
 - Results in life-threatening illness or injury;
 - Results in a permanent impairment of a body structure or a body function;
 - Requires in-subject hospitalization or prolongation of existing hospitalization;
 - Results in medical or surgical intervention to prevent life-threatening illness or injury or permanent impairment;
- Congenital defect or anomaly

Note: Elective hospitalizations for pre-treatment conditions (e.g., elective cosmetic procedures, cataract removal) are not serious adverse events (SAE).

Each AE/SAE is considered to be either anticipated or unanticipated as described below.

CONFIDENTIAL AND PROPRIETARY DATA: This document and the information contained herein may not be reproduced, used, or disclosed without written permission from Edwards Lifesciences LLC

7.4 ANTICIPATED ADVERSE EVENTS

As with all prosthetic heart valves, serious complications, sometimes leading to death, are associated with the use of tissue valves as well as the replacement procedure. In addition, complications due to individual subject reaction to an implanted device, or to physical or chemical components, particularly those of biological origin, may occur at varying intervals (hours or days) necessitating reoperation and replacement of the prosthetic device.

Known risks associated with the use of stented bioprosthetic heart valves include:

- Allergic reaction to valve materials
- Angina
- Annulus (damage, dissection, tear)
- Aortic Insufficiency –Regurgitation/Stenosis
- Aorta (damage, dissection, tear)
- Blood - Coagulopathy
- Blood - Hemolysis
- Blood - Hemorrhage/anemia
- Blood Pressure alteration (hypotension, hypertension)
- Cardiac Arrest
- Cardiac Arrhythmias/conduction disturbances
- Cardiac Failure (heart failure)
- Chordae Tendineae damage (Mitral valve)
- Coronary artery Ostia blockage
- Death
- Endocarditis
- Explant
- Infection – local
- Neurologic Events
 - Stroke (CVA)
 - Transient Ischemic Attack (TIA)
- Reduced exercise tolerance
- Thromboembolism
- Transvalvular or Valvular Leaking
- Valve instability/ migration/ embolization
- Valve dislodgement
- Valve - Non structural dysfunction
 - Paravalvular Leak
 - Leaflet impingement (Aortic or Mitral valve)
 - Leaflet tissue damage (instruments /sutures or pannus)
 - Subject Prosthesis Mismatch (PPM) (due to inappropriate sizing)
 - Distortion at implant
- Valve - Structural dysfunction/deterioration (e.g., wear, leaflet tear, calcification, leaflet detachment from stent posts, component deterioration – physical or chemical)
- Valve - Thrombosis
- Valve Wireform and or Frame Fracture or Distortion (from chest compression or trauma)
- Valve stent fracture
- Valve stent separation
- Annulus frame fracture
- Annulus frame separation

Potential risks associated with aortic valve replacement surgery include:

- Allergic reaction
- Annular dissection
- Aortic or arterial dissection
- Asystole and/or cardiac arrest
- Bleeding
 - Peri- or post-procedural
 - Anticoagulant related
 - Pericardial tamponade
 - Hematoma
 - Cerebral vascular
- Cardiogenic shock
- Disseminated intravascular coagulation (DIC)
- Embolism, pulmonary
- Esophageal tear/rupture
- Heart failure
- Hypo- or hypertension
- Hypoxemia
- Infection, local or wound or systemic
- Infection, Septicemia – bacterial, viral, fungal
- Myocardial infarction
- Myocardial perforation, free wall
- Multi-system organ failure (MOF)
- Pericardial effusion
- Pleural effusion
- Pulmonary edema
- Pneumonia
- Renal failure, acute
- Respiratory failure
- Thrombocytopenia, (Non-HIT)
- Thrombocytopenia, heparin induced (HIT)
- Thromboembolism
 - Venous, peripheral or central
 - Arterial, peripheral or central
 - Pulmonary, thrombus or other

Based on a review of the scientific literature, preliminary animal studies, risk analysis and a Failure Modes and Effects Analysis (FMEA), other potential risks associated with the use of the trial valve include:

- Loss of frame structural integrity resulting in damage to LVOT
- Delivery system impingement resulting in mitral leaflet chordae trauma or damage
- Annular frame damage or under-flaring resulting in a reduction of EOA
- Annular frame overexpansion resulting in conduction interruptions or disturbances (i.e., arrhythmia)
- Separation of the annular frame from the sewing ring
- Mitral valve impingement or abrasion with or without mitral regurgitation
- Insufficient frame expansion/suturing resulting in PVL requiring intervention or reoperation
- Device malpositioning resulting in coronary ostial blockage
- Device embolization into the aorta or ventricle

7.5 UNANTICIPATED ADVERSE DEVICE EFFECT

An unanticipated adverse device effect (UADE) is defined as any serious adverse event on health and safety, or any life-threatening problem or death caused by, or associated with, this device, if that event, problem, or death was not previously identified in nature, severity, or degree of incidence in the investigational plan, or application. Additionally, an unanticipated adverse event includes any other unanticipated serious problem associated with a device that relates to the rights, safety, or welfare of subjects.

The Investigator must submit to the Sponsor or its designee and to the reviewing IRB, a report of any UADE occurring during this clinical investigation as soon as possible, but under no circumstance, later than 10 working days after the Investigator first learns of the event. Full and complete written documentation must follow this report. The Investigator must document all UADE, including the time and date of onset, complete description of the event, severity, duration, actions taken and outcome. Record all UADE on the appropriate CRF.

The Sponsor will immediately conduct an evaluation of any unanticipated device-related event. In addition, the Sponsor will notify the DMC of an UADE within five (5) business days after Edwards or its designee first receives notice of the event.

7.6 ADVERSE EVENT DEFINITIONS/ REPORTABLE EVENTS

Since assessment of safety requires comparison of the occurrence of adverse events to the OPC, it is extremely important to provide definitions of adverse events and to adhere to these definitions. The method of reporting shall conform to the most recently published *“Guidelines for reporting mortality and morbidity after cardiac valve interventions”* by Akins et al [14].

In addition, it is of utmost importance to determine the primary event since secondary morbid events will not be included in the calculation of any complication rates. However, secondary events will be reported for informational purposes. For example, if a subject has endocarditis and develops a PVL secondary to the infection, the PVL will not be counted in the PVL rate. The endocarditis will be included in the calculation of the endocarditis rate.

CONFIDENTIAL AND PROPRIETARY DATA: This document and the information contained herein may not be reproduced, used, or disclosed without written permission from Edwards Lifesciences LLC

Multiple events of the same complication in the same subject will be counted as a single event if the complication does not resolve. For example, if a subject experiences multiple TIAs in a two-week period, only one event will be included in the linearized rate, although all events will be reported as a cluster. Similarly, if a subject exhibits a PVL at six months, and that leak remains at the POD 365-415 visit, only one event will be included in the linearized rate calculation. If, however, a subject has a stroke and then 6 months later experiences another stroke, both events will be included in the calculation of the linearized stroke rate.

MORTALITY REPORTING:

In the event of subject death, every effort should be made to obtain a copy of the autopsy report and/or death summary. The Investigator will provide information about the cause of death and will determine relationship to the clinical investigational device. The Clinical Events Committee (CEC) will adjudicate each death for device relatedness and procedure relatedness. The site will send the Sponsor copies of an autopsy report, if available, and/or a death summary.

If explant of a device occurs during autopsy, return the device to the Sponsor for analysis. Return kits for explanted devices will be provided upon request by the clinical site manager.

EXPLANT REPORTING:

In the event a trial valve is explanted in the late post-operative period, the Investigator will provide information on the explant and determine the relationship to the trial valve. Every effort should be made to supply copies of available explant reports, to the Sponsor. As soon as possible, explanted trial valves should be returned to the Sponsor for analysis. Sponsor will provide “return kits” for explanted devices upon request by the clinical site manager.

A complete list of Adverse Event Definitions/ Reportable Events is located in XXX.

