9.1.2.1 Primary Safety Endpoints

For the safety endpoints listed in Section 2.1, the early adverse events within 30 days of implant will be reported as the number of events divided by the number of patients for the events. Linearized rates will be used to summarize adverse events for the late (>30 days) post-operative period. The linearized rates will be calculated as the number of late events divided by the total late-patient years.

Actuarial analysis using the Kaplan-Meier method will be used to estimate the probability of freedom from each primary safety endpoint. Primary analyses of the primary safety endpoints (post 30 days) will be based on linearized rates, which account for multiple

events from a single patient. Actuarial (Kaplan-Meier) analysis of the time to first event per patient will be provided as an additional analysis.

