9.1.2.2 Other Safety Data

Percentages for the early events and linearized rates for the late events will be calculated for all complications. If valve malposition, valve instability, valve dislodgement or valve migration/embolization occurs, any consequent adverse events or procedures (e.g. coronary ostia blockage, mitral valve impingement, or abrasion, intraoperative intervention, or reoperation) will be noted and rates presented.

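### Do the rates for consequent events in Section 9.1.2.2 break the rule in Section 7.6 that keeps secondary events out of complication rates?

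*Combined protocol and SAP*

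**What the plan says.** Section 7.6 sets two counting rules.

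- **Secondary events.** The primary event must be identified, because "secondary morbid events will not be included in the calculation of any complication rates". The example is a paravalvular leak caused by endocarditis: the endocarditis counts in its rate and the leak does not count in the leak rate. The section adds: "However, secondary events will be reported for informational purposes".
- **Repeat events.** For an unresolved complication that recurs in one subject, "only one event will be included in the linearized rate".

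Section 9.1.2.1 defines three summaries for the safety endpoints listed in Section 2.1: early percentages, late linearized rates (the primary analysis after 30 days), and Kaplan-Meier curves "used to estimate the probability of freedom from each primary safety endpoint", which are an additional analysis of time to first event. It does not cite 7.6.

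Section 9.1.2.2, on other safety data, calculates percentages and linearized rates for all complications. If a valve-position event occurs, then "any consequent adverse events or procedures (e.g. coronary ostia blockage" and other examples, ending with "intraoperative intervention, or reoperation) will be noted and rates presented".

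Section 7.2 notes that "A procedure is not an AE, but the reason for the procedure may be an AE". Section 7.1 has the Clinical Endpoints Committee "decide on safety endpoints which will be included in the final analysis".

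**The concern.** Section 7.6 excludes secondary events from every complication rate, and 9.1.2.2 promises rates for events that are secondary by their own description. Neither section refers to the other. The note in 7.2 on procedures may take reoperation outside the exclusion, but blockage of a coronary ostium after malposition is an adverse event, so the clash remains for that example.

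Two further questions follow. First, if the exclusion applied to linearized rates but not to Kaplan-Meier curves, the two analyses of one endpoint would use different events. A subject whose leak followed endocarditis would be absent from the leak rate but would fail on the leak curve. Second, reoperation and explant usually follow some other event. A strict reader could call them secondary and drop them, which would bring two listed primary safety endpoints close to zero whatever was observed.

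Section 7.6 itself stresses correct identification of the primary event because safety is judged against objective performance criteria. It is therefore reasonable to ask whether the counting rule is clear where the rates are defined.

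**Working it through.** The plan states no figure for this point, so the check is mainly a comparison of the sections, followed by the size of one event.

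**1. Section 7.6 against 9.1.2.2.** The leak example in 7.6 shows what is excluded: a secondary event may not enter the rate of the endpoint it resembles. The following sentence permits informational reporting and does not restrict it to counts or listings. Section 9.1.2.2 stands apart from the primary endpoint section, applies only if a valve-position event occurs, and describes the consequences of that event. Showing how often malposition led to ostial blockage puts nothing into a primary endpoint rate. Both instructions can be followed together.

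**2. Reoperation, explant and death.** Section 9.1.2.1 applies its summaries to the endpoints in Section 2.1. That list includes all-cause mortality, reoperation and explant, each with a valve-related subset, so each has its own rate. The exclusion covers secondary morbid events. Section 7.2 says a procedure is not an adverse event, and Section 7.7 records reoperation or explant of the trial valve as an action taken and lists death and explant as outcomes. Treating them as secondary would empty endpoints that the plan lists, and all-cause mortality by its name cannot leave out deaths that follow another event.

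**3. Kaplan-Meier.** Only the repeat-event rule is worded for the linearized rate. It has little bearing on a time-to-first-event curve, which uses one event per subject. The secondary-event exclusion carries no such limit. Section 7.1 has one committee decide which safety endpoints enter the final analysis, which points to one adjudicated event set for both methods.

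**4. Size of one event.**

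Inputs from the documents: 934 enrolled (Synopsis); enrolment from 26 September 2012 to 25 August 2016, which is 3.91 years (Section 1.1); follow-up until the last subject reaches five years (Section 4.1).

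Assumptions: uniform enrolment; 85 to 100% implanted, so N = 794 to 934; constant attrition hazard h of 3, 5 or 8% per year.

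Potential follow-up T runs from 5 to 8.91 years, with mean 5 + 3.91/2 = 6.96. Late patient-years = N × the average over T of [exp(−h × 30/365.25) − exp(−h × T)]/h.

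| N | h = 3% | h = 5% | h = 8% |
|---|---|---|---|
| 934 | 5,773 | 5,390 | 4,879 |
| 794 | 4,908 | 4,582 | 4,148 |

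- Late linearized rate, per event: 100/5,773 = 0.017 to 100/4,148 = 0.024 per 100 patient-years.
- Kaplan-Meier, per event at time t: about 100/[N × exp(−h × t)] percentage points. Lowest (N = 934, h = 3%, day 30): 0.107. Highest (N = 794, h = 8%, year 5): 0.188.
- Early percentage, per event: 100/934 = 0.107 to 100/794 = 0.126 points.

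For comparison, at the 800 late patient-years that triggered the premarket analysis, one event was worth 100/800 = 0.125 per 100 patient-years. That analysis is complete, and Section 9.0 limits the current section to work after approval.

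**The case for a change.** The strongest case for a change is that the literal conflict is real. One section excludes secondary events from any rate, another gives rates for all complications, and nothing links them. The reporting scheme in Section 7.7 treats reoperation, explant and death as following from an adverse event, and 9.1.2.2 names reoperation among the consequent procedures. Two analysts could code the endocarditis-related leak differently for the Kaplan-Meier curve, and clarifying sentences would cost almost nothing.

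Part of this stands. The rates in 9.1.2.2 are not labelled as descriptive, and 9.1.2.1 does not state that the secondary-event rule extends to Kaplan-Meier. No sentence says that a reoperation or explant counts whatever event led to it, although the endpoint list leaves no other workable reading.

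The rest is weaker. The silence is established only for the text available here. The full event definitions, the reference to the detailed analyses and the committee charter are not in the public document, and 7.6 also defers to a published reporting guideline. Any of these may state the rule, and text withheld from the public version cannot be treated as missing from the plan. Section 9.1.2 sets no post-approval test or threshold that one reclassified event could cross. The per-event sizes above describe any event in a trial of this size and are not evidence of an error.

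**Conclusion.** No change follows. The plan already gives a workable analysis: 7.6 governs the primary endpoint rates, 9.1.2.2 adds descriptive information about valve-position events, and mortality, reoperation and explant have their own rates. The remaining gap is a label and a cross-reference, which analysts working from one adjudicated event set would supply in the same way.

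The effect is small: 0.017 to 0.024 per 100 patient-years for each late event, about 0.11 to 0.19 points on a Kaplan-Meier estimate within five years, and 0.11 to 0.13 points for each early event. These figures rest on the assumed implant fraction, attrition and uniform enrolment. The number of events affected is unknown. Neither bias nor a different conclusion has been shown.
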